Language updated to remove rationale for unipolar VAS administration. Language updated to include alertness/drowsiness VAS not sedation VAS.  Section 10.5, pp. 56 and 57	Based on FDA feedback, the Drug Liking VAS will be administered as a bipolar scale; therefore, rationale for use of unipolar Drug Liking VAS was removed. Alertness/Drowsiness VAS was added and sedation VAS removed, this was an error in the original protocol.
Additional safety measures and withdrawal section separate into 2 subsections, Section 10.6.1 Opioid Effects and Section 10.6.2 Treating Opioid Withdrawal. The following details on treating opioid withdrawal were added as follows:  If opioid withdrawal occurs after dosing with CAM2038 q1w (precipitated withdrawal), the following assessments will be collected every 4 hours while the subject is awake for at least 24 hours after dosing to include:  1) COWS, 2) OOWS, 3) VAS assessment of opioid withdrawal severity.  Treatment will be based upon clinical judgment of the medically responsible physician at each site. To ensure the safety of subjects, incidences of precipitated withdrawal in response to CAM2038 q1w will be followed carefully and an amendment of the protocol to ensure subjects are	

Version: 2.0, 17NOV2015 Page 9 of 99

Change and Location Within the Protocol	Rationale
in a more advanced state of opioid withdrawal e.g.,	
increase required COWS score from 8 to 12, to reduce the	
risk of BPN-related precipitated withdrawal, will be	
considered if more than one incidence occurs.	
Ancillary medications that will be made available for	
symptomatic relief of all episodes of withdrawal	
(precipitated by CAM2038 q1w and other) are summarized in Table 5.	
56646H 10.0.2, pp. 50	D 1 112 1 1 1
Statistical analysis was updated to further define the way	Based on additional review by the
in which TEAEs would be displayed. The following text was updated:	statistics group it was determined that the TEAEs would be displayed by CAM2038
During the Qualification Phase subjects TEAEs will be	dose and by hydromorphone relevant dose
displayed by IR morphine 30 mg treatment or by	since specific time of AE may not be
hydromorphone treatment groups i.e., 0 mg 6 mg or	available.
18 mg - on the days of hydromorphone challenges.	
During the Treatment Phase, TEAEs will be displayed	
by CAM2038 q1w relevant dose and hydromorphone	
relevant dose i.e., 0 mg 6 mg or 18 mg – on the days of	
hydromorphone challenges. TEAEs will be displayed	

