Before each scheduled IR morphine 30 mg dose is administered, research/nursing staff will record oxygen saturation and respiratory rate and assess the subject for sedation and/or intoxication. If respiratory rate drops to <12 breaths per minute or oxygen saturation is <95%, the measurements will be repeated and recorded. If either oxygen saturation or respiratory rate remains outside parameters or the subject appears sedated or intoxicated, the oral maintenance dose will be withheld and a study Investigator notified. The withheld dose may be administered later (and the administration time recorded) once it is determined that the subject's status has returned to within a safe range. Continuous pulse oximetry and telemetry can be implemented at the Investigator's discretion.

m Pulse oximetry/Cardiac monitoring/Respiratory rate monitoring will be included on each Hydromorphone Challenge Session day (i.e., Days -3, -2, -1, 1, 2, 3, 4, 5, 6, 8, 9, 10, 11, 12, and 13). Monitoring will be continuous from pre-dose up to 5 hours post-dose or longer, if clinically indicated. After each dose of hydromorphone, subject's oxygen saturation, respiratory rate, and overall safety profile will be reviewed by the research/nursing staff to determine whether it is safe to proceed with administration of the next dose of hydromorphone.

<sup>n Includes temperature, blood pressure, pulse rate, respiratory rate.

On each Hydromorphone Challenge Session day (i.e., Days -3, -2, -1, 1, 2, 3, 4, 5, 6, 8, 9, 10, 11, 12, and 13), vital signs will be collected predose and at 15, 30, 45, 60, 90, 120 and 180 minutes post-dose and then hourly up to 5 hours post-dose.

P On CAM2038 q1w dosing days (i.e., Days 0 and 7), vital signs will be collected at pre-dose and at 15, 30, and 60 minutes post-dose, then hourly up to 6 hours post-dose.

	Screening	Inpatie	Inpatient Qualification Phase			Inpatient Treatment Phase				
Visit:	1				2					
Day:	-39 to -11	-10, -9, -8, -7, OR -6	-9, -8, -7, -6, OR -5 to -4	-3 to -1	0	1 to 3 & 4 to 6	7	8 to 10 & 11 to 13	14/ ET	21
Adverse Events q	X	X	X	X	X	X	X	X	X	X
C-SSRS (baseline/screening)	X									
C-SSRS (since last visit) r			X		X		X		X	
MADRS s	X		X		X		X		X	
COWSt	X	X	X	X	Xu	X	X u	X	X	
oows				X	Xu	X	X u	X	X	
CAM2038 Injection Site Examination					X	X	X	X	X	
Oral IR Morphine 30 mg Dosing v		X	X	X						
CAM2038 q1w SC Injection w					X		X			

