#### 10.4.7. Cardiac Monitoring (including Pulse Oximetry)

Cardiac monitoring (cardiac rhythm, heart rate) and pulse oximetry will be performed from inpatient check-in to the end of the Treatment Phase (or Early Termination) of the study. Data will not be recorded in the database, but will be used for real-time safety monitoring. Occurrences of oxygen saturation <95%, the measurements will be repeated and recorded as AEs. Pulse oximetry/cardiovascular monitoring will be included on each Hydromorphone Challenge Session day (i.e., Day -3, -2, -1, 1, 2, 3, 4, 5, 6, 8, 9, 10, 11, 12, and 13). Monitoring will be from pre-dose until at least 5 hours post-dose or longer, if clinically indicated. Cardiac monitoring and pulse oximetry equipment may be removed briefly (for hygiene purposes), as needed.

Continuous pulse oximetry and telemetry can be performed if the Investigator deems it is necessary.

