#### 12.3.4.1. Adverse Events

Adverse events will be coded by system organ class (SOC) and preferred term using the Medical Dictionary for Regulatory Activities (MedDRA) reporting system. Treatment-emergent AEs are defined as any of the following:

- Non-serious AEs with onset on the date of first dose of treatment with the study drug through discharge or Early Termination, whichever occurs first;
- Serious AEs with onset on the date of first dose of treatment with the study drug through 30 days after discharge or Early Termination, whichever occurs first;
- AEs that start before the start of treatment but increase in severity or relationship at the time of or following the start of treatment through discharge or Early Termination, whichever occurs first.

The number and percentage of subjects with TEAEs will be displayed for each treatment group. During the Qualification Phase subjects TEAEs will be displayed by IR morphine 30 mg

Version: 2.0, 17NOV2015 Page 72 of 99

treatment or by hydromorphone treatment groups i.e., 0 mg 6 mg or 18 mg - on the days of hydromorphone challenges. During the Treatment Phase, TEAEs will be displayed by CAM2038 q1w relevant dose and hydromorphone relevant dose i.e., 0 mg 6 mg or 18 mg - on the days of hydromorphone challenges. TEAEs will be displayed by SOC and preferred term. Additionally, TEAEs will be tabulated for each treatment group by severity and by relationship to the study drug. A listing of SAEs will be provided if applicable.

If an AE is considered to be caused by a drug, the Investigator will note which drug caused the AE.

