11.2 ADVERSE EVENTS

Each AE and SAE term recorded on the case report forms (CRFs) by primary system organ class (SOC) and will be mapped to a preferred term using the MedDRA dictionary. The investigator will assess AE severity and relationship to the study treatment.

A treatment emergent adverse event (TEAE) is defined as any AE with an onset date on or after date of randomization, or any ongoing event on the date of first dose that worsens in severity after date of randomization. Only TEAEs with an onset date prior to date of last dose + 30 days will be tabulated in summary tables. For the purpose calculating treatment emergence and inclusion in summary tables, incomplete onset dates will be imputed as detailed in Appendix B.

AEs will be summarized by the number and percent of subjects in each primary SOC and preferred term. Patients will be counted only once for each primary SOC and each preferred term. Summary tables of AEs by primary SOC, preferred term and intensity will be provided. If a subject has more than one AE coded to the same preferred term, the subject will be counted only once for that preferred term by using the event with the highest intensity. Similarly, if a subject has more than one AE within a primary SOC category, the subject will be counted only once in that SOC category by using the event with the highest intensity. AEs by primary SOC, preferred term and relationship to study drug will be provided as well. If a subject has more than one AE coded to the same preferred term, the subject will be counted only once for that preferred term by using the most related event. Similarly, if a subject has more than one AE within a primary SOC category, the subject will be counted only once in that primary SOC category by using the most related event. In addition, serious adverse events (SAE) by primary SOC and preferred term will be provided. Deaths and SAEs will be summarized similarly to AEs. All adverse event tables will also include the total number of events, counting multiple events per patient.

AEs will be presented by treatment group (CAM2038 q1w of 24 mg or 32 mg and by hydromorphone treatment groups i.e., 0 mg 6 mg or 18 mg – during qualification period- and CAMP2038 relevant dose/hydromorphone relevant dose – on the days of hydromorphone challenges) and overall. An AE will

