be attributed to a hydromorphone dose, if the AE occurred within one hour of the dosing (if the time of the AE is missing, the AE will be attributed to CAM2038). Summaries of these AE subsets will be presented for the following categories:

- Study drug related
- Intensity
- Relationship to injection (Suspected or Not Suspected)
- Suspected to be study drug related by intensity
- Serious
- AEs which led to discontinuation
- SAEs which led to discontinuation
- AEs occurring in 5% or greater of any treatment group (by preferred term)

In the AE summary, preferred terms within each SOC will appear in alphabetical order.

Frequencies for deaths and hospitalizations will also be summarized by treatment group and overall.

Other safety analyses will be performed as appropriate

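### The one-hour and missing-time rule in SAP 11.2 sits against the challenge-day display of adverse events and could thin the hydromorphone columns of four safety tables

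*SAP*

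**What the plan says.** **Protocol 12.3.4.1.** In the Treatment Phase, "TEAEs will be displayed by CAM2038 q1w relevant dose and hydromorphone relevant dose", the latter on challenge days. No time window is attached. The same section adds: "If an AE is considered to be caused by a drug, the Investigator will note which drug caused the AE".

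**Protocol, Summary of Changes.** The reason given for this display is that it was chosen "since specific time of AE may not be" available.

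**SAP 11.2, display.** The SAP repeats the day-based layout: "CAMP2038 relevant dose/hydromorphone relevant dose – on the days of hydromorphone challenges".

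**SAP 11.2, next sentence.** An AE goes to a hydromorphone dose if it "occurred within one hour of the dosing (if the time of the AE is missing, the AE will be attributed to CAM2038"). The SAP then announces summaries of the subsets so formed. Intensity and relationship to study drug are among the listed categories.

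**SAP Appendix A.** Four tables cross hydromorphone with a CAM2038 dose: 14.3.3.1.2 and 14.3.3.1.3 (intensity, 24 mg and 32 mg) and 14.3.4.1.2 and 14.3.4.1.3 (relationship, 24 mg and 32 mg).

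**Data and monitoring.** Protocol 10.4.1.1 lists onset and resolution dates among the AE data and names no clock time. Protocol 10.4.7 says of challenge days: "Monitoring will be from pre-dose until at least 5 hours post-dose or longer, if clinically indicated". It also says: "Occurrences of oxygen saturation <95%, the measurements will be repeated and recorded as AEs". Table 4 of the protocol schedules vital signs on those days at "15, 30, 45, 60, 90, 120 and 180 minutes post-dose and then hourly up to 5 hours post-dose".

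**The concern.** SAP 11.2 gives two rules for deciding whether an AE appears with a hydromorphone dose. One uses the calendar day. The other uses the clock, with a fallback when the clock time is absent. They need not give the same counts, and the SAP does not say which one fills the columns.

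The clock rule also depends on the item that, by the protocol's own account, may be unavailable. Its window is short against the period in which subjects are watched and in which a low oxygen saturation is to be recorded as an AE.

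What is at stake is a stated secondary objective (SAP 4.1): the safety and tolerability of CAM2038 given together with hydromorphone. The four tables above are the planned AE displays by hydromorphone dose within each CAM2038 group. If their hydromorphone columns omit AEs that arose on challenge days, the combination may look better tolerated than the data show.

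**Working it through.** The plan states no figure to reproduce here, so the check sets the texts side by side and counts what the documents allow.

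**1. One AE under both rules.** Take an AE with no recorded time, on an 18 mg challenge day, in the 32 mg group.

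- Day-based display (Protocol 12.3.4.1 and SAP 11.2): CAM2038 32 mg plus hydromorphone 18 mg.
- Attribution sentence (SAP 11.2): CAM2038.

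Now take an AE timed at 90 minutes after the same injection. The day-based display again gives CAM2038 32 mg plus 18 mg. Under the attribution sentence it falls outside the hour.

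**2. Three readings.** Let *m* be the share of challenge-day AEs with no time, and *p* the share of timed ones that start within one hour.

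| Reading of the attribution sentence | AEs leaving the hydromorphone columns | Share |
|---|---|---|
| It does not govern the columns of the four tables | none | 0 |
| It governs them, but the hour does not exclude later timed AEs | untimed | *m* |
| It governs them, and the hour decides (the natural reading) | untimed, and timed after 1 hour | 1 − *p*(1 − *m*) |

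The sentence about summarising the subsets follows directly on the rule. Its categories include intensity and relationship, the two classifications used in the four tables. That favours the second or third reading over the first, but does not settle it.

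**3. Scope.** Tables 14.3.2 to 14.3.10 make 13 AE tables: 1 for the qualification period, 4 for hydromorphone with CAM2038, and 8 for CAM2038 doses and overall (1 + 4 + 8 = 13). The 4 are affected. Treatment Phase challenge days are Days 1–6 and 8–13, so 6 + 6 = 12.

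**4. The window against the schedule.**

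- Monitoring: 1 h / 5 h = 20% of the minimum monitored period, which leaves 80% outside.
- Vital signs after dosing: 15, 30, 45, 60, 90, 120, 180, 240 and 300 minutes, so 9 checks. At or before 60 minutes: 4. After 60 minutes: 5.

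These are counts of scheduled observation, not of AEs.

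**5. Illustration only.** The documents give neither *p* nor *m*. Both are assumed here, under the third reading.

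| *m* | share moved at *p* = 0.8 | share moved at *p* = 0.2 |
|---|---|---|
| 0 | 1 − 0.8 = 20% | 1 − 0.2 = 80% |
| 0.25 | 1 − 0.8 × 0.75 = 40% | 1 − 0.2 × 0.75 = 85% |
| 0.5 | 1 − 0.8 × 0.5 = 60% | 1 − 0.2 × 0.5 = 90% |
| 1 | 100% | 100% |

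Under the second reading the share is simply *m*. The result runs from nothing to everything depending on unknown inputs, so no estimate is offered.

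**The case against.** The strongest defence has three parts.

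First, neither document defines the relevant hydromorphone dose, and the attribution sentence can be read as that definition. Protocol 12 leaves derivations and the handling of missing data to the SAP and allows methods to be revised. This stands as a matter of authority: the SAP may set such a rule. It does not remove the ambiguity, because the SAP restates the day-based layout and then adds the clock rule without saying that one qualifies the other.

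Second, presenting and attributing are different acts. An untimed AE could be attributed to CAM2038 and still be printed in the combined challenge-day column. Appendix A gives titles and no layouts, so this cannot be excluded. For that reason the point is conditional. A reader might infer that untimed AEs must leave the hydromorphone columns however the sentence is read; the text does not go that far.

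Third, the consequences are modest. Protocol 12.3.4 plans no formal safety comparisons, the rule is the same for 0, 6 and 18 mg, the AEs remain in the overall CAM2038 tables and in the AE listing, and the investigator's causal-drug note is still recorded. All of this stands.

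A reader might also infer that no AE times exist, so that every AE would go to CAM2038. The list in Protocol 10.4.1.1 says what will be included and need not be exhaustive. SAP version 1.01 removed certain summaries that lacked data yet the rule is still there, which suggests that some times were collected.

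**Conclusion.** The point holds in conditional form. If the attribution sentence governs the four hydromorphone-with-CAM2038 tables, as the sentence after it suggests, untimed challenge-day AEs would be missing from the hydromorphone columns. On the natural reading, AEs that start after the first hour would be missing too. That departs from the display in Protocol 12.3.4.1 and from the layout that SAP 11.2 has just repeated.

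The scope is 4 of 13 AE tables. The number of AEs affected is unknown. It would be wrong to read the 20% window, or the 5 of 9 later vital-sign checks, as an estimate of the under-count, since AE onset need not follow the observation schedule. It would also be wrong to say that AEs are lost, because they are only placed elsewhere. No efficacy result or formal claim depends on these tables. The change is still worth making, because it is cheap and the tables serve a secondary objective.

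**What to change.** In Tables 14.3.3.1.2, 14.3.3.1.3, 14.3.4.1.2 and 14.3.4.1.3, replace the one-hour and missing-time rule with the protocol's display:

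- Every AE with onset on a Treatment Phase challenge day (Days 1–6 and 8–13) is shown under the CAM2038 dose plus that day's hydromorphone dose, whether or not a time was recorded.
- An AE with onset on any other day, such as Day 0, 7 or 14, is shown under CAM2038 alone.
- The investigator's causal-drug assessment stays in the relationship tables.
- Any table based on the one-hour window is a supplement and is labelled as such.

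Do not add a rule that carries pre-injection AEs back to the previous day's dose. The protocol has none. It would make placement depend on the clock again. If confined to challenge days, it would treat early-morning AEs on Days 7 and 14 differently from those on Days 2–6 and 9–13, although all of these days follow a hydromorphone injection.

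The cost is SAP wording and the programming of four tables, with no new data. The small downside is that AEs which began before the morning injection (about 9:00 am, Protocol 9.5) appear under that day's dose, for 0, 6 and 18 mg alike.

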11.3 LABORATORY ASSESSMENTS

Chemistry, Hematology, Urinalysis and Coagulation Profile will be assessed at baseline and Week 24 (see Section 10.4.3 for a complete list of parameters to be assessed). Summary statistics for these parameters will be presented by visit for the actual value and change from baseline for each test in each laboratory category (Hematology, Chemistry, Urinalysis, and Coagulation Profile). Shift tables will be presented for shifts from baseline lab categories to end of study laboratory category. The three laboratory categories will be: L (below lower bound of normal range), N (within normal range), and H (above higher bound of normal range).

If a lab value is reported using a non-numeric qualifier (e.g., less than (<) a certain value, or greater than (>) a certain value), the given numeric value will be used in the summary statistics, ignoring the non-numeric qualifier.

If a subject has repeated laboratory values for a given time point, the value from the first evaluation at that time point will be used for summarization purposes. For the purpose of determining baseline, the last nonmissing observation on or prior to randomization will be used. The Week 24 values will be the last post-baseline value on or prior to Week 24.

11.4 COLUMBIA SUICIDE SEVERITY RATING SCALE (CSSR-S)

Summary of Columbia Suicide Severity Ratings will be provided by CAM2038 group and by the scheduled day the measurements are obtained.

11.5 MONTGOMERY-ASBERG DEPRESSION RATING SCALE (MADRS)

Summary of Montgomery-Asberg Depression Rating will be provided by CAM2038 group and by the scheduled day the measurements are obtained.

11.6 VITAL SIGNS

Vital signs will consist of blood pressure (systolic and diastolic blood pressure, mmHg), pulse rate (beats per minute), and respiratory rate (breaths/min), and oxygen saturation (%) collected while sitting, following a rest period of at least 3 minutes. Vital sign values and change from baseline in the vital signs will be summarized for each treatment group.

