4.0 STUDY DESCRIPTION

4.1 STUDY OBJECTIVES

The primary objective of this study is:

- To evaluate the degree of opioid blocking effects of CAM2038 q1w following administration of intramuscular (IM) hydromorphone (6 mg and 18 mg) compared to administration of 0 mg IM hydromorphone (placebo) on subjective opioid effects in subjects with opioid use disorder, as measured by the Drug Liking visual analog scale (VAS).

The secondary objectives of this study are:

- To evaluate the degree of opioid blocking effects of CAM2038 q1w following administration of IM hydromorphone (6 mg and 18 mg) compared to administration of 0 mg IM hydromorphone (placebo) on subjective opioid effects in subjects with opioid use disorder, as determined by the secondary outcome measures.
- To explore the relationship between plasma buprenorphine (BPN) concentration and blockade of the subjective opioid effects of hydromorphone.
- To examine the safety and tolerability of CAM2038 q1w when co-administered with hydromorphone.

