4.2 STUDY TREATMENTS

In this study, subjects will be randomized to one of two treatment groups in a 1:1 ratio to receive either CAM2038 1qw 24 mg or CAM2038 1qw 32 mg. Subjects within both CAM2038 1qw dosing groups will be randomized to one of 6 sequences of ordered hydromorphone challenge sessions: A/B/C, A/C/B, B/A/C, B/C/A, C/A/B, and C/B/A, where A, B, and C denote hydromorphone 0 mg, 6 mg, and 18 mg.

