Following the 3-day Qualification/Baseline Hydromorphone Challenge Session (Days -3 to -1), eligible subjects will be randomized in a 1:1 ratio to one of 2 groups to receive CAM2038 q1w at doses of 24 mg or 32 mg, stratified by gender. Subjects will receive two, once weekly injections of CAM2038 q1w, 7 days apart, (injections on Day 0 and Day 7) and will remain inpatient in the CRU for a total of approximately 3 weeks, during which time, 1 qualification/baseline Hydromorphone Challenge session will occur prior to CAM2038 administration then 4 Hydromorphone Challenge Sessions (3 consecutive days each with dose randomized) will be conducted on Days 1 to 3, Day 4 to 6, Days 8 to 10, and Days 11 to 13 after the first CAM2038 administration. Each Hydromorphone Challenge Session will consist of 3 doses of hydromorphone 10 mg/mL IM injections (doses of 0 mg [placebo], 6 mg and 18 mg) administered on 3 consecutive days in randomized order. Eligible subjects will be randomized in a 1:1:1:1:1:1 ratio to 1 of 6 treatment sequences according to two 3×3 William squares. The following treatment sequences will be used: ABC, ACB, BAC, BCA, CAB, and CBA, where A, B, and C are IM hydromorphone doses, 0 mg (placebo), 6 mg, and 18 mg, respectively. The doses, 0 mg (placebo), 6 mg or 18 mg, will be administered once daily during the hydromorphone challenge sessions. Safety assessments will be conducted immediately following each dose of hydromorphone administered in each Challenge Session and scheduled pharmacodynamic evaluations will occur over approximately 5 hours post dose. Plasma BPN and norbuprenorphine (NorBPN) levels will also be obtained approximately 60 minutes prior to hydromorphone dosing (predose) on each day of the Hydromorphone Challenge Sessions.

Subjects will be discharged on Day 14 and a follow-up phone interview will be conducted on Day 21. The degree of hydromorphone dose tolerability will be determined based on the site-specific study Investigator's review of the subject's oximetry data, vital signs, behavior, and physical demeanor.

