9.6 POWER AND SAMPLE SIZE JUSTIFICATION

A sample size of 24 subjects will provide 90% power for the CAM2038 32 mg to demonstrate no significant difference in the mean E_{\max} score of the Drug Liking VAS comparing to 0 mg hydromorphone at a two-sided 0.05 significance level with a non-significant difference cutoff at ≤ 11 points. In the sample size calculation it was assumed that the true difference was less than or equal to 1.5 and the standard deviation was 9.8.

Additional 24 subjects will be enrolled to CAM2038 24 mg group. This sample size will provide approximately 83% power for the CAM2038 24 mg to demonstrate no significant difference in the mean E_{\max} score of the Drug Liking VAS comparing to 0 mg hydromorphone at a two-sided 0.05 significance level with a non-significant difference cutoff at ≤ 11 points. In the sample size calculation it was assumed that the true difference was less than or equal to 2.5 and the standard deviation was 9.8.

The plan will be to enroll a sufficient number of subjects to ensure that approximately 48 subjects complete the study (24 subjects per treatment group) by over-enrollment as needed.

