TABLE 14.3.8	Summary of All Adverse Events That Lead to Study Discontinuation by System Organ Class and Preferred Term for CAM2038 Doses and Overall (Safety Population)
TABLE 14.3.9	Summary of All Serious Adverse Events That Lead to Study Discontinuation by System Organ Class and Preferred Term for CAM2038 Doses and Overall (Safety Population)
TABLE 14.3.10	Summary of All Deaths and Hospitalizations for CAM2038 Doses and Overall (Safety Population)
TABLE 14.4	Summary of Columbia Suicide Severity Ratings by CAM2038 Doses and Time

	(Safety Population)
TABLE 14.5	Summary of Montgomery-Asberg Depression Rating by CAM2038 Doses and Time (Safety Population)
TABLE 14.6.1.1	Summary of Clinical Hematology Data by CAM2038 Doses and Time (Safety Population)
TABLE 14.6.1.2	Shift from Baseline in Laboratory Tests: Hematology by CAM2038 Doses (Safety Population)
TABLE 14.6.2.1	Summary of Clinical Chemistry Data by CAM2038 Doses (Safety Population)
TABLE 14.6.2.2	Shift from Baseline in Laboratory Tests: Chemistry by CAM2038 Doses (Safety Population)
TABLE 14.6.3.1	Summary of Clinical Coagulation Profile Data by CAM2038 Doses (Safety Population)
TABLE 14.6.3.2	Shift from Baseline in Laboratory Tests: Coagulation Profile by CAM2038 Doses (Safety Population)
TABLE 14.6.4	Number (%) of Patients with Abnormal Physical Examination Findings by CAM2038 Doses (Safety Population)
TABLE 14.6.5	Summary of Vital Signs by CAM2038 Doses at Each Visit (Safety Population)
TABLE 14.6.6	Summary of 12-Lead ECG Conclusions by CAM2038 Doses (Safety Population)
TABLE 14.6.7	Summary of 12-Lead ECG Individual Parameters by CAM2038 Doses (Safety Population)

List of Listings

Number	Title
LISTING 16.2.1	Patient Meets Inclusion Criteria
LISTING 16.2.2	Eligibility for Randomization
LISTING 16.2.3	Patient Randomization
LISTING 16.2.4.1	Demographics
LISTING 16.2.4.2	Medical History
LISTING 16.2.4.3	Psychiatric History
LISTING 16.2.5.1	CAM2038 Injection
LISTING 16.2.5.2	Injection Site Examination/ Treatment Compliance
LISTING16.2.6.1	COWS, C-SSRS, MADRS, and OOWS Scales
LISTING16.2.6.2	VAS Scales
LISTING16.2.7.1	Adverse Events
LISTING16.2.7.2	Serious Adverse Events
LISTING16.2.7.3	Adverse Events That Lead to Study Drug Discontinuation
LISTING16.2.7.4	Adverse Events That Have Death as the Outcome
LISTING16.2.7.1	Death Report
LISTING16.2.7.1	Prior and Concomitant Medications/Procedures
LISTING16.2.8.1	Lab Test Samples
LISTING16.2.8.2	Clinical Hematology
LISTING16.2.8.3	Clinical Chemistry

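### The only planned vital-sign summary is by CAM2038 group and visit, with no pre-specified split by hydromorphone dose or time after dose, so it dilutes a hydromorphone effect and shows no 0 mg comparator

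*SAP*

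**What the plan says.** SAP 11.6 gives the whole vital-sign analysis in one sentence: "Vital sign values and change from baseline in the vital signs will be summarized for each treatment group". SAP 4.2 uses the term for the CAM2038 arms, with subjects "randomized to one of two treatment groups in a 1:1 ratio" (24 mg or 32 mg). SAP Appendix A lists one vital-sign table, 14.6.5, titled "Summary of Vital Signs by CAM2038 Doses at Each Visit (Safety Population". Protocol 12.3.4.3 asks for descriptive statistics, including minimum and maximum, and adds no split by hydromorphone dose or time.

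The collection schedule follows the hydromorphone injection. Under Protocol Table 4, on every challenge day "vital signs will be collected predose and at 15, 30, 45, 60, 90, 120 and 180 minutes post-dose", and then hourly to 5 hours. SAP 6.1 takes baseline as the last value up to the date of randomization, or an average where there are several.

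SAP 4.1 (like Protocol 6.2) lists this secondary objective: "To examine the safety and tolerability of CAM2038 q1w when co-administered with hydromorphone". For adverse events the SAP does separate the challenge doses: SAP 11.2 presents them "by hydromorphone treatment groups i.e., 0 mg 6 mg or 18 mg", and several Appendix A adverse-event tables combine hydromorphone with each CAM2038 dose.

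**The concern.** The co-administration objective asks what hydromorphone does to a subject who already has CAM2038 on board. For vital signs, the direct evidence is the difference between 18 mg or 6 mg and 0 mg in the same subject, in the hours after injection. The crossover supplies that contrast and the readings are timed to capture it, but the planned table averages over the dose and does not commit to showing the time.

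Protocol 10.6.1 names respiratory depression among the more serious possible effects of buprenorphine and hydromorphone. A respiratory-rate change after 18 mg is the kind of finding this schedule can detect. A report that follows the SAP literally could show small mean changes by CAM2038 group when a larger change had occurred at one hydromorphone dose.

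**Working it through.** The plan states no figure on this point, so there is none to reproduce. The check counts readings and doses and follows what the stated grouping does to a dose effect.

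**1. Readings (Protocol Table 4).** Pre-dose (1), then 15, 30, 45, 60, 90, 120 and 180 minutes (7), then 240 and 300 minutes (2): 1 + 7 + 2 = 10 per challenge day. Treatment Phase challenge days are 1–6 and 8–13, which is 12 days. So 10 × 12 = 120 timed readings per subject for each vital sign.

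**2. Dose mix on a challenge day.** SAP 4.3: "Eligible subjects will be randomized in a 1:1:1:1:1:1 ratio to 1 of 6 treatment sequences according to two 3×3 William squares". With A = 0 mg, B = 6 mg and C = 18 mg:

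| Day of session | 0 mg | 6 mg | 18 mg |
|---|---|---|---|
| 1 | ABC, ACB | BAC, BCA | CAB, CBA |
| 2 | BAC, CAB | ABC, CBA | ACB, BCA |
| 3 | BCA, CBA | ACB, CAB | ABC, BAC |

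Each dose fills each day in 2 of 6 sequences, or one third. SAP 9.6 plans "24 subjects per treatment group". With exact balance that is 24/6 = 4 per sequence and 2 × 4 = 8 subjects on each dose, every day.

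**3. Dilution of the mean.** Let the mean shift relative to 0 mg be D at 18 mg and r × D at 6 mg. The CAM2038-by-day mean then shifts by (0 + rD + D)/3 = (1 + r)D/3.

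| Assumed 6 mg effect | r | Shift shown in the table |
|---|---|---|
| None | 0 | D/3 |
| Half of the 18 mg effect | 0.5 | D/2 |
| Same as the 18 mg effect | 1 | 2D/3 |

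The documents give no value for r. As an assumed illustration, a fall of 3 breaths/min at 18 mg would appear as 1.0 to 2.0 breaths/min. If a day's time points are also averaged, readings before or well after the effect shrink it further. That part cannot be sized, because the documents contain no table shell.

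**4. Comparator and extremes.** All three doses fall in the same cell, so there is no 0 mg column. The minimum and maximum survive pooling, but without the dose at which they occurred.

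**5. Baseline.** SAP 6.1 fixes baseline at or before randomization. A change on Day 12, for example, therefore also contains the CAM2038 effect and any drift since then. The same morning's pre-dose reading would isolate the change after the injection.

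**6. What a split would give.** Pooled over four treatment sessions, each hydromorphone dose in each CAM2038 group has 24 subjects and 24 × 4 = 96 subject-days, each subject with their own 0 mg days. The cell count is 2 CAM2038 doses × 3 hydromorphone doses × 10 times = 60 per vital sign. Keeping all five sessions apart would need 60 × 5 = 300, with about 8 subjects per dose per day.

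**The case against.** The strongest reply is that the SAP text is open rather than wrong. SAP 11.6 does not restrict its grouping to CAM2038, SAP 11.2 speaks of hydromorphone treatment groups, and SAP 11.0 presents safety variables by study drug received, which could include hydromorphone. SAP 11.2 also closes by allowing further safety analyses where appropriate. This has some force for the text alone, but the title of Table 14.6.5 names CAM2038 doses only, while the adverse-event tables name hydromorphone where it is meant. None of these clauses pre-specifies a split.

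Second, respiratory safety is partly covered elsewhere. Protocol 10.4.7 has saturations below 95% recorded as adverse events, and adverse events are tabulated by hydromorphone dose. That stands, with a limit: SAP 11.2 attributes an event to hydromorphone only within one hour of dosing and assigns events without a time to CAM2038, whereas vital signs run to 5 hours.

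Third, the table is descriptive, no formal safety comparison is planned, and D/3 is the extreme case, since Protocol 9.4 describes the challenge doses as supratherapeutic. All true, which is why the range to 2D/3 is given.

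Three stronger readings are tempting but unsupported:
- A reader might infer that the trial cannot show the co-administration effect, or that the crossover contrast is thrown away. Listing 16.2.8.8 keeps every value by subject, and further analyses remain possible.
- A reader might infer from the visit row of Protocol Table 4 that the whole inpatient stay is one visit and will be pooled. That header is damaged in the available text and cannot carry the claim. The dilution holds even if each visit is one day.
- A reader might infer that respiratory rate is the only respiratory measure to be analysed. SAP 11.6 lists oxygen saturation among the vital signs, although Protocol 10.4.5 omits it and Protocol 10.4.7 keeps the monitoring data out of the database.

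**Conclusion.** The point holds as a defect in the planned summary. SAP 11.6 and Table 14.6.5 together specify a grouping that pools the three hydromorphone doses. They name neither dose nor post-dose time, and they measure change from a value that predates CAM2038 treatment.

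The mean effect of 18 mg is shown at one third to two thirds of its size before any averaging over time. This rests on balanced sequences within each CAM2038 group and on a 6 mg effect between none and equal to that of 18 mg. Exact thirds will not hold in the Safety Population if there are dropouts, but the pooling remains. The primary endpoint is unaffected. The change should be made before database lock, because afterwards any dose-by-time table would be post hoc.

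**What to change.** In SAP 11.6 and Table 14.6.5:
- Tabulate challenge-day vital signs by CAM2038 dose × hydromorphone dose (0, 6, 18 mg) × nominal post-dose time, pooled over the four treatment sessions, as value and as change from the same-day pre-dose reading. State the number of subjects as well as the number of subject-days.
- Show the Qualification session in the same layout, as the reference without CAM2038.
- Add each subject's minimum post-dose respiratory rate, summarised by hydromorphone dose.
- Include oxygen saturation if it is recorded, and reconcile SAP 11.6 with Protocol 10.4.7 on whether it is.
- Keep the by-day CAM2038 table for Days 0, 7 and 14/ET, where no hydromorphone is given.

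The cost is SAP wording, a revised shell and more table pages: 60 cells per vital sign for the treatment phase, plus the Qualification session. No new data collection is needed unless oxygen saturation turns out not to be recorded and the sponsor wants it summarised.
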